8.2.3 Sample Collection and Handling Instructions

Blood samples (2 – 3 ml) will be collected in SST tubes at a site distant from the infusion for pharmacokinetic evaluation. **NOTE:** Patients \leq 23 kg should only have 2 ml of blood drawn per sample. Samples cannot be drawn from the 2nd lumen of a multi-lumen catheter through which drug is being administered. Record the exact time that the sample is drawn along with the exact time that infusion begins and ends.

8.2.4 Sample Processing

1. Collect blood into a 2 – 3 mL SST tube and invert the tube several times prior to allowing blood to clot.
2. Allow blood to clot for at least 60 minutes at room temperature.
3. Separate serum within 60 – 90 minutes of collection.
4. Centrifuge for 10 minutes at room temperature at 1100 – 1300 x g

THIS PROTOCOL IS FOR RESEARCH PURPOSES ONLY, SEE PAGE 1 FOR USAGE POLICY

5. Transfer serum equally into two 2 mL cryovials (primary and back up)
6. Immediately freeze at -60 °C to -80 °C.

8.2.5 Sample Labeling

Each tube must be labeled with the patient's study registration number and the study I.D. Data should be recorded on the Pharmacokinetic Study Form ([Appendix VI-A](#), [Appendix VI-B](#), and [Appendix VI-C](#)), which must accompany the sample(s).

Additionally, MacroGenics has standard naming conventions for samples. MGD006 is flotetuzumab. Sites should use the below labeling conventions for lab samples:

Pre MGD006 PK 1 (primary)
Pre MGD006 PK 2 (back up)
UNS PK (use this for unscheduled)

For all patients being treated on DL1, samples are to be labeled via the following conventions:

Sample Timepoint	Label Naming Convention
Cycle 1, Day 1: prior to start of infusion	Pre MGD006 infusion PK
Cycle 1, Days 3 – 7: 30 minutes prior to syringe change and dose escalation	30 min pre MGD006 infusion (include day) PK
Cycle 1, Day 8: 24 hours after Day 7 syringe change and final dose escalation	Day 8 PK
Cycle 1, Day 12, Day 15, Day 19, Day 22, Day 27, and Day 29 (prior to infusion ending): any time	Day 12 PK, Day 15 PK, etc.

For all patients being treated on DL-1, samples are to be labeled via the following conventions:

Sample Timepoint	Label Naming Convention
Cycle 1, Day 1: prior to start of infusion	Pre MGD006 infusion PK
Cycle 1, Day 4, Day 6, and Day 8: 30 minutes prior to syringe change and dose escalation	30 min pre MGD006 infusion (include day) PK
Cycle 1, Day 9: 24 hours after Day 8 syringe change and final dose escalation	Day 9 PK
Cycle 1, Day 13, Day 17, Day 21, Day 25, and Day 29 (prior to infusion ending): any time	Day 13 PK, Day 17 PK, etc.

For all patients being treated on DL2, samples are to be labeled via the following conventions:

Sample Timepoint	Label Naming Convention
Cycle 1, Day 1: prior to start of infusion	Pre MGD006 infusion PK
Cycle 1, Days 3 – 8: 30 minutes prior to syringe change and dose escalation	30 min pre MGD006 infusion (include day) PK
Cycle 1, Day 9: 24 hours after Day 8 syringe change and final dose	Day 9 PK

escalation	Cycle 1, Day 13, Day 17, Day 21, Day 25, and Day 29 (prior to infusion ending): any time	Day 13 PK, Day 17 PK, etc.
------------	--	----------------------------

Blood samples will also be collected at the following time points on the patient's last day of protocol therapy (EOT = end of treatment):

Sample Timepoint	Label Naming Convention
30 minutes, 1 hour, 2 hours, 4 hours, 8 hours, and 24 hours after the end of infusion	EOT PK 30 min post, EOT PK 1 hr post, etc.

8.2.6 Sample Shipping Instructions

Store samples at -70°C until shipment. Ship on dry ice to MacroGenics as each patient completes the cycle or at site's discretion. If PK and immunogenicity samples are shipped in the same shipping container, place the PK and immunogenicity samples in separate cryoboxes within the shipping container. Prior to sample shipment, please email [REDACTED] to alert [REDACTED] them of the sample shipment. Ship to the following address:

A horizontal bar chart consisting of four solid black bars of increasing length from left to right. The bars are separated by small gaps.

NOTE: Primary and back-up aliquots from the same time point should NOT be sent in the same shipment.

8.3 Immunogenicity Study (Required)

8.3.1 Description of Studies and Assay

Serum samples will be collected and anti-flotetuzumab antibodies will be detected using a validated bridging immunoassay by a MacroGenics, Inc. bioanalytical lab. Immunogenicity will be compared between patients who achieve CR/CRi and those who do not.

8.3.2 Sampling Schedule (See Appendix VII)

Blood samples will be collected at the following time points for all patients:

- Cycle 1, Day 1: pre-infusion
- Cycle 3, Day 1: pre-infusion
- Cycle 5, Day 1: pre-infusion

8.3.3 Sample Collection and Handling Instructions

Blood samples (2 – 3 ml) will be collected in SST tubes at a site distant from the infusion for immunogenicity evaluation. **NOTE:** Patients ≤ 23 kg should

THIS PROTOCOL IS FOR RESEARCH PURPOSES ONLY, SEE PAGE 1 FOR USAGE POLICY
only have 2 ml of blood drawn per sample.

8.3.4 Sample Processing

1. Collect blood into a 2 – 3 mL SST tube and invert the tube several times prior to allowing blood to clot
2. Allow blood to clot for at least 60 minutes at room temperature.
3. Separate serum within 60 – 90 minutes of collection.
4. Centrifuge for 10 minutes at room temperature at 1100 – 1300 x g.
5. Transfer serum equally into two 2 mL cryovials (primary and back up).
6. Immediately freeze at -60 °C to -80 °C.

8.3.5 Sample Labeling

Each tube must be labeled with the patient's study registration number, the study I.D., and the date and time the sample was drawn. Data should be recorded on the Pharmacokinetic Study Form ([Appendix VII](#)), which must accompany the sample(s).

Additionally, MacroGenics has standard naming conventions for samples. Sites should use the below labeling conventions for lab samples:

Pre MGD006 ADA

UNS ADA (use this for unscheduled)

For all patients, samples are to be labeled via the following conventions:

Sample Timepoint	Label Naming Convention
Cycle 1, Day 1: pre-infusion Pre MGD006 infusion	Pre MGD006 ADA
Cycle 3, Day 1: pre-infusion Pre MGD006 infusion C3	C3 Pre MGD006 ADA
Cycle 5, Day 1: pre-infusion Pre MGD006 infusion C5	C5 Pre MGD006 ADA

8.4 Baseline CD123 Site Density Quantification (Optional)

8.4.1 Description of Studies and Assay

Baseline bone marrow samples will be used to analyze CD123 site density on AML cells to aid in identifying biomarkers of therapy response and resistance. Correlation between changes in CD123 expression and patient's clinical response to flotetuzumab as well as cytogenetic/molecular features will be described. Samples will be analyzed at Hematologics, Inc.

8.4.2 Sampling Schedule (See Appendix VIII)

Analyses will be performed on the bone marrow samples retrieved prior to Cycle 1.

While the preferred specimen is bone marrow, if bone marrow samples cannot be obtained, peripheral blood may be sent in for patients who have an absolute blast count $\geq 1,000/\mu\text{L}$.

8.4.3 Sample Collection and Handling Instructions

Bone marrow samples (5 mL) will be collected in a preservative-free sodium heparin vacutainer (green top).

In cases where the specimen is expected to take more than 24 hours to arrive, please add equal volume of RPMI 1640 medium to the marrow specimen.

If peripheral blood is obtained, 10 mL of blood will be collected in a preservative-free sodium heparin vacutainer (green top).

8.4.4 Sample Labeling

Each tube must be labeled with the patient's study registration number, the study I.D., the date and time the sample was drawn, and must be clearly labeled as bone marrow aspirate (BMA), if applicable. Data should be recorded on the Baseline CD123 Site Density Quantification Study Form ([Appendix VIII](#)), which must accompany the sample(s).

8.5 NGS MRD Comparison with Flow Cytometry MRD (Optional)

8.5.1 Description of Studies and Assay

MRD levels at each bone marrow evaluation time point will be measured by standard flow cytometry and compared to MRD measured by NGS. The correlation between the measurements with each technique will be described to

THIS PROTOCOL IS FOR RESEARCH PURPOSES ONLY, SEE PAGE 1 FOR USAGE POLICY
aid in identifying biomarkers of therapy response and resistance.

8.5.2

Sampling Schedule (See Appendix IX)

Bone marrow samples will be collected from consenting patients at the following time point:

- With each bone marrow evaluation

While the preferred specimen is bone marrow, if bone marrow samples cannot be obtained prior to Cycle 1, peripheral blood may be sent in for patients who have an absolute blast count $\geq 1,000/\mu\text{L}$. Bone marrow may be substituted for peripheral blood for the sample taken prior to Cycle 1 ONLY. All other samples must be bone marrow.

8.5.3

Sample Collection and Handling Instructions

Bone marrow samples (10 – 15 mL) will be collected in green top sodium heparin tubes at the time of bone marrow evaluation.

If peripheral blood is obtained for the prior to Cycle 1 time point, 20 – 30 mL of blood will be collected in large purple EDTA tubes. **NOTE:** Patients $\leq 23\text{ kg}$ should only have 20 mL of blood drawn per sample.

8.5.4

Sample Processing

Store samples at 4°C until shipment.

8.5.5

Sample Labeling

Each tube must be labeled with the patient's study registration number, the study I.D., and the date and time the sample was drawn. Data should be recorded on the NGS MRD Comparison with Flow Cytometry MRD Study Form ([Appendix IX](#)), which must accompany the sample(s).

8.5.6

Sample Shipping Instructions

For questions regarding sample collection, processing, and shipping, please email [REDACTED]

Samples may be shipped at room temperature or with an ice pack. If samples are to be shipped with an ice pack, the collection tubes are to be wrapped in paper towels or other insulation to minimize tube freezing and direct contact with the ice pack.

Prior to sample shipment, please email [REDACTED] to alert them of the sample shipment.

Ship samples to the following address:

[REDACTED]
[REDACTED]
[REDACTED]
[REDACTED]

Following sample shipment, send another email to the addresses listed above

THIS PROTOCOL IS FOR RESEARCH PURPOSES ONLY, SEE PAGE 1 FOR USAGE POLICY

with the Fed-Ex tracking number and copy the PEPN1812 Research Coordinator on the email.

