If a patient experiences progressive disease at any time point, they must discontinue protocol therapy. Patients with at least a partial response (PR) following Cycle 2 may continue on subsequent cycles of flotetuzumab for a total of up to 6 cycles. Patients should discontinue protocol therapy if they have not achieved at least a PR following Cycle 2. No planned step-up dosing will occur during subsequent cycles unless there is an infusion interruption of > 3 days between cycles of flotetuzumab. For patients with no evidence of disease after Cycle 1, subsequent cycles should be interrupted until ANC $\geq 500 \mu\text{L}$ and platelets $\geq 20,000/\text{mm}^3$. Patients with persistent disease are permitted to continue flotetuzumab regardless of ANC and platelet counts.

Pharmacokinetic sampling and monitoring for ADAs will be performed in all patients (see [Appendix VI-A](#), [Appendix VI-B](#), [Appendix VI-C](#), and [Appendix VII](#)). In consenting patients, correlative studies to characterize the tumor microenvironment will be obtained, which will include peripheral blood studies and bone marrow (see [Appendix X](#) and [Appendix XII](#)). Correlative plasma studies as a measurement of CRS and biomarkers of response will also be obtained in consenting patients (see [Appendix XI](#)).

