- j. Bone marrow aspirate. Prior to Cycle 1 and at the end of Cycle 1.
- k. Urinalysis. Prior to Cycle 1.
- l. Pregnancy test. Prior to Cycle 1 for women of childbearing potential.
- m. ECHO or gated radionuclide study. Prior to Cycle 1.

THIS PROTOCOL IS FOR RESEARCH PURPOSES ONLY, SEE PAGE 1 FOR USAGE POLICY

- n. EKG. Prior to Cycle 1.
- o. Neurologic exam. Prior to Cycle 1.
- p. Ht/Wt/BSA. Prior to Cycle 1.
- q. NGS MRD comparison with flow cytometry MRD. In consenting patients only at the time of bone marrow evaluation. See [Section 8.5](#) for details.
- r. CD3 T-lymphocyte quantification. In consenting patients, blood samples will be collected on Cycle 1 Days 1, 8, 15, 22, and 29. See [Section 8.6](#) for details.
- s. Cytokine production measurement. In consenting patients, blood samples will be collected on Cycle 1, Day 1 (prior to flotetuzumab infusion), and on Cycle 1, Day 8. Additionally, if patients experience IRR/CRS, blood samples will be collected from consenting patients at the time of IRR/CRS and at the time of IRR/CRS resolution. See [Section 8.7](#) for details.
- t. Immunogenicity study. One sample to be collected from all patients on Cycle 1, Day 1 (pre-infusion). See [Section 8.3](#) for details.
- u. Tumor microenvironment profiling. Prior to Cycle 1. See [Section 8.8](#) for details.
- v. Clot section/biopsy. Prior to Cycle 1 and at the end of Cycle 1. To be performed in conjunction with the bone marrow aspiration.
- w. CD123 site density analysis. In consenting patients prior to Cycle 1. To be performed on the collected bone marrow aspirate. See [Section 8.4](#) for details.
- x. Cytogenetics and FISH. Prior to Cycle 1. To be performed on the collected bone marrow aspirate. It is recommended that cytogenetics/FISH be performed by a COG-approved laboratory.
- y. Flow cytometry with MRD determination. At the end of Cycle 1 with bone marrow evaluation.

This listing only includes evaluations necessary to answer the primary and secondary aims. OBTAIN OTHER STUDIES AS REQUIRED FOR GOOD CLINICAL CARE.

Comments

(Include any held doses, or dose modifications)

THIS PROTOCOL IS FOR RESEARCH PURPOSES ONLY, SEE PAGE 1 FOR USAGE POLICY

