APPENDIX IX: NGS MRD COMPARISON WITH FLOW CYTOMETRY MRD STUDY FORM

COG Pt ID # _____ Cycle 1, Day 1 Date: _____

Please do not write patient names on this form or on samples.

Patient Weight: _____ kg

Flotetuzumab Dose Level: _____ nanograms/kg/day Flotetuzumab Total Daily Dose: _____ nanograms

Bone marrow samples (10 – 15 ml) will be collected from consenting patients at the time of each bone marrow evaluation.

Record the exact time the bone marrow sample is collected at the end of each cycle.

Bone Marrow Sample No.	Scheduled Collection Time	Actual Date Sample Collected	Actual Time Sample Collected (24-hr clock)
1	Prior to Cycle 1	/ /	____:____
2	At the end of Cycle 1	/ /	____:____
3	At the end of Cycle 2	/ /	____:____
4	At the end of Cycle 3	/ /	____:____
5	At the end of Cycle 4	/ /	____:____
6	At the end of Cycle 5	/ /	____:____
7	At the end of Cycle 6	/ /	____:____

One copy of this NGS MRD Comparison with Flow Cytometry MRD Study Form should be uploaded into RAVE. A second copy should be sent with the samples to the address listed in [Section 8.5.6](#). See [Section 8.5](#) for detailed guidelines for packaging and shipping NGS MRD Comparison with Flow Cytometry MRD samples.

Signature: _____ Date: _____
(site personnel who collected samples)

THIS PROTOCOL IS FOR RESEARCH PURPOSES ONLY, SEE PAGE 1 FOR USAGE POLICY

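### Section 8.5.1 names only a correlation for the NGS-versus-flow MRD comparison; no agreement measure is planned, and the handling of repeated marrows is not specified

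*Combined protocol and SAP*

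**What the plan says.** Section 8.5 of the combined protocol and SAP is an optional sub-study whose title announces a comparison of NGS MRD with flow MRD. Section 8.5.1 states: "MRD levels at each bone marrow evaluation time point will be measured by standard flow cytometry and compared to MRD measured by NGS". It then names its summary, "The correlation between the measurements with each technique will be described", and gives the purpose, which is to "aid in identifying biomarkers of therapy response and resistance".

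Sampling under Section 8.5.2 is from consenting patients, at one recurring occasion: "With each bone marrow evaluation". The Appendix IX form has seven rows, from before Cycle 1 to "At the end of Cycle 6". Flow MRD starts later. Its pre-study cell in the Section 8.1 table is blank, and the Cycle 1 therapy delivery maps (Appendices IV-A to IV-C) read "Flow cytometry with MRD determination. At the end of Cycle 1 with bone marrow evaluation".

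Sections 2.5 and 5.1 limit who reaches the later marrows: "Patients should discontinue protocol therapy if they have not achieved at least a PR following Cycle 2".

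No bias estimate, limits of agreement, positive/negative agreement, positivity threshold or rule for undetectable values appears in Section 8.5. Section 11.5 has no MRD-specific method and describes the correlative analyses as descriptive, exploratory and hypothesis-generating.

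**The concern.** When two assays are run on the same marrow, the useful result is whether they say the same thing: how far apart the values are, and how often one assay calls MRD positive when the other calls it negative. A correlation answers a different question, namely whether the two sets of values rise and fall together. It can be close to 1 while one assay reads several-fold higher throughout. It also has no natural place for undetectable results, which are the ones that decide who is MRD-negative.

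If the report gave only a high correlation, a reader could take the assays as interchangeable without evidence of it. MRD status matters as a category in this protocol. Under Section 5.5.2, detectable leukemia, with MRD included, makes a child unevaluable for hematological DLT, and that section does not say which assay decides.

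A second, smaller gap is the unit of analysis. A child can give several pairs, and Section 8.5 does not say whether the summary is by time point, by child or over all pairs.

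**Working it through.** **Number of pairs per child (from the documents).**
- NGS samples: Appendix IX has 7 rows. Volume check: 7 × 10 ml = 70 ml and 7 × 15 ml = 105 ml, which reproduces the 70–105 ml in Appendix II.
- Flow MRD: scheduled at the end of Cycles 1 to 6, with none pre-study.
- Scheduled pairs: at most 6 per child, all post-treatment. A child who stops after Cycle 2 without a PR gives at most 2.

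The documents state no sample size, precision or agreement target for this comparison, so there is no further plan figure to reproduce.

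**What a constant offset does (assumed inputs).** Let T be the true log10 MRD with SD 1.0. Let flow = T + error and NGS = T + b + error, with independent errors of SD e in each assay. None of these values is in the documents. Here e is 0.2 or 0.4, and b is 0, 0.5 or 1.0 log10 (1.0 being ten-fold).

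- Correlation: r = 1/(1 + e²). The offset b does not appear. For e = 0.2, r = 1/1.04 = 0.96. For e = 0.4, r = 1/1.16 = 0.86.
- SD of the difference: e√2, which is 0.283 or 0.566.
- Limits of agreement: b ± 1.96·e√2.
- Lin's concordance: 2/(2(1 + e²) + b²). For e = 0.2 and b = 1.0, this is 2/3.08 = 0.65.
- Share of pairs within 3-fold: Φ((0.477 − b)/(e√2)) − Φ((−0.477 − b)/(e√2)), since log10 3 = 0.477.

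| e | b (log10) | r | Concordance | Limits of agreement (log10) | Within 3-fold |
|---|---|---|---|---|---|
| 0.2 | 0 | 0.96 | 0.96 | −0.55 to 0.55 | 91% |
| 0.2 | 0.5 | 0.96 | 0.86 | −0.05 to 1.05 | 47% |
| 0.2 | 1.0 | 0.96 | 0.65 | 0.45 to 1.55 | 3% |
| 0.4 | 0 | 0.86 | 0.86 | −1.11 to 1.11 | 60% |
| 0.4 | 0.5 | 0.86 | 0.78 | −0.61 to 1.61 | 44% |
| 0.4 | 1.0 | 0.86 | 0.60 | −0.11 to 2.11 | 17% |

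Simulation gives the same correlations, concordances and limits to within 0.01.

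**Effect on classification (more assumptions).** Take e = 0.2 and one cut-off of 0.1% for both assays. The share of flow-negative marrows that NGS calls positive rises as follows when b goes from 0 to 1.0:
- mean MRD 1%: from 17% to 85%
- mean MRD 0.1%: from 9% to 67%
- mean MRD 0.01%: from 3% to 40%

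The size depends heavily on the mean, which the documents do not give. The direction is the same throughout, and r is 0.96 in all six cases.

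**The case against.** **The purpose is biomarkers, not assay agreement.** Section 8.5.1 gives biomarker identification as its reason, so assay interchangeability is partly the reviewer's question. That is fair, and it lowers the stakes. But the section's title and first sentence set up a comparison of two assays, and reading either as a response marker requires knowing whether they call the same marrow alike.

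**The protocol uses the word correlation loosely.** Sections 8.4.1, 8.6.1 and 11.5 use it for association in general, including with categorical features, and 8.5.1 names no coefficient. A cross-table is therefore not excluded. It is not planned either, and even a loosely described association need not report bias or positive/negative disagreement.

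**Offset and threshold can cancel.** If each assay has its own cut-off, a constant offset need not cause misclassification. This is true, and it is a reason to tabulate the calls directly, since a correlation shows neither outcome.

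**A stronger reading that fails.** A reader might infer that all pairs are pooled, so that several marrows from one child count as separate evidence and a few responders dominate. The documents do not say this. Section 8.5.1 speaks of each marrow time point, which fits a by-cycle summary at least as well, and Section 11.5 plans no interval or test. If someone did pool and attach a standard 95% interval, simulated coverage with 3 samples from each of 12 or 24 children and a true correlation of 0.6 would be about 93% to 79% as within-child correlation goes from 0.3 to 0.8. Those inputs are assumed and the analysis is not a planned one, so this is a reason to state the unit of analysis and not evidence of an error.

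**Conclusion.** The point holds in a limited form. Correlation is the only summary named for a two-assay comparison, and it cannot reveal a systematic difference between the assays. With an assumed true log10 SD of 1.0 and error SD of 0.2, a ten-fold offset leaves it at 0.96 while agreement within 3-fold drops from 91% to 3%. With error SD 0.4 the drop is from 60% to 17%, at an unchanged 0.86. The insensitivity to an offset is algebraic; the percentages rest on assumed assay errors and offsets.

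How up to six scheduled pairs per child enter the summary is left open. That is silence, not a stated plan to pool them.

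The sub-study is optional and exploratory, matches none of the aims listed in Sections 1.1 to 1.3, and the correlation feeds no decision rule. The effect on the primary aims is nil. This is a worthwhile, low-cost improvement and nothing more serious.

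**What to change.** Keep the correlation in Section 8.5.1 as a secondary description and add:

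1. At the end of Cycle 1, with one pair per child, a 2×2 table of MRD positive/negative by assay. Use a positivity threshold stated in advance for each assay, and report positive and negative percent agreement with exact 95% intervals. Undetectable results then count as negatives and are not lost.
2. For pairs quantifiable on both assays, the mean log10 difference and limits of agreement, with the number of pairs left out because either result was below detection.
3. For later cycles, the same summaries given descriptively by cycle and not pooled across cycles.

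The text should also say whether a pre-Cycle 1 pair is intended, since NGS is sampled then but flow MRD is not scheduled.

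The cost is wording and the choice of two thresholds; samples and assays stay the same. The drawback is imprecision. The number consenting is not given, but if 10 flow-positive children all agreed on NGS, the exact 95% interval would run from 0.025^(1/10) = 69% to 100%. With 9 of 10 it would be 55% to 99.7%.
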